1. SYNOPSIS

Study Objective	To assess and compare tissue aggregation and visualization of two (2) Hyaluronic Acid fillers via ultrasound
Methodology	Randomized, split-face, subject-blinded, comparative study
Number of Subjects at the end	15 subjects to complete
Study duration	24 weeks
Test products	Restylane Contour Juvéderm Voluma
Conditions of use	Per on-label instruction
Study visits	Day 0, week 4, and week 24
Specific Inclusion Criteria:	
 ○ Demographics and study skin conditions - Any race and ethnicity (to be recorded) - Fitzpatrick skin type (to be recorded) - Women or men - Age: 22 to 65 years old - Subject with midface volume loss and contour deficiency ○ Administrative - Ability of giving consent for participation in the study - Agreement to adhere to the procedures and requirements of the study and to report to the institute on the day(s) and at the time(s) scheduled for the assessments.
Specific Exclusion Criteria:	
 ○ Skin conditions - History of allergy or hypersensitivity to lidocaine and/or injectable hyaluronic acid (HA) - Previous permanent or semi-permanent implant in proposed treatment area - Previous biodegradable tissue augmentation therapy in the proposed treatment area within 12 months prior to the baseline visit

Protocol Version 2:

This document contains confidential, proprietary information.

	
 - History of other facial treatment/procedure at the study area (midface) in the previous 6 months that would potentially interfere with study injections (e.g., facial surgery, oral surgery, resurfacing, mesotherapy, lipolytic injections, botulinum toxin injections)

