7.5 Treatments Administered

The study products contain lidocaine hydrochloride, but additional topical or local anesthesia or ice pack may be used at the discretion of the Investigator to enhance the experience of the subjects. Any additional topical or local anesthesia used will be recorded in the CRFs.

The injection tools (needles or cannulas) will be determined at the discretion of the Investigator. However, for each subject, the Investigator must use the same type of injection tool to perform injection for both sides of the face. Switching device within the subject will not be allowed in order to avoid any inconsistent comparison. Either needles or cannulas will be used per subject. The brand name, gauge and length of the cannulas and incision needles used by the Investigator will be recorded in the CRFs.

The study products will be injected into the midface at the supraperiosteal to subcutaneous layer in the prezygomatic space lateral to the plane of the medial canthus, along the plane of the zygomatic arch ~1cm medial to hairline (described in Figure 1 below).

Protocol Version 2:

This document contains confidential, proprietary information.

[figure not shown]

Figure 1. Description of injection boundary.

The amount of each study products needed varies between subjects and within subjects bilaterally, given the natural asymmetry of the face. However, subjects will be treated to optimal correction of the midface as agreed by the Investigator and subjects. The product volume injected during each treatment session for each subject will be recorded in the CRFs.

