8.1 Visits and Examinations

8.1.1. Screening/Baseline/Day 0 Visit (Visit 1)

1. Subjects will report to the testing clinical at D0 for baseline screening.
2. Prior to beginning of any study related activities, subjects will be informed about the purpose and nature of the study, the expected post-treatment events, and the potential risks involved with the treatments.
3. Subjects will be given an informed consent form, HIPAA form, photography release form, and Code of Conduct form to read.
4. Once subjects have completed reading, they will be interviewed to ensure their understanding of the aforementioned forms and be given the opportunity to ask any study related questions.
5. Subjects who agree to sign the aforementioned forms will be asked to complete a demographic information, medical history form, and concomitant medication form. Subjects declining to sign any of the forms will be dismissed from the study.
6. Subjects will be screened and qualified on the basis of the subject inclusion and exclusion criteria. Subjects failing to meet criteria will be dismissed from the study.
7. Subjects will have the below assessments by Investigator or a trained Clinic staff:
 - a. Clinical 2D photography by VISIA at neutral expression (3/4 left, front, 3/4 right), at closed-mouth smile (3/4 left, front, 3/4 right), and at open-mouth maximum smiling (3/4 left, front 3/4 right)
 - b. Clinical 3D photography by Vectra at neutral expression of full face
 - c. Ultrasound on each cheek at neutral expression and at maximum smiling (left and right). Note: ultrasound assessment will be performed at the same area of the injection.
8. Clinic staff or Investigator will assign the appropriate test treatment to each side of the face based on the predetermined computer-generated randomization.
9. Investigator will instruct the subjects on each treatment administration procedure and perform the treatments.
10. Investigator or Clinic staff will record the details of the administration, amount of each treatment used for each cheek and any subsequent adverse events (AEs) in the CRF.
11. Immediately post-injection, subjects will have the below assessment by Investigator:
 - a. Ultrasound on each cheek at neutral expression and at maximum smiling (left and right). Note: ultrasound assessment will be performed at the same area of the injection.
12. Subjects will be instructed on any standard care post-treatment and when to contact the Investigator in case of emerging AEs.

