10. STATISTICAL ANALYSIS

Data of completing subjects will be included for all statistical analyses. Descriptive statistical summary will be performed including N, mean, median, standard deviations, minimum, and maximum of values at all applicable time points and for both treatments.

For each study treatment, mean of the change from baseline will be estimated at applicable post-baseline time point. The null hypothesis, that the mean change from baseline is zero, will be tested using methods described in the Statistical Analysis Plan table.

The following will be calculated and reported for each evaluation parameter at applicable post-baseline time point:

$$\text{Percent mean change from baseline} = \frac{(\text{visit mean score} - \text{baseline mean score})}{\text{baseline mean score}} \times 100$$

$$\text{Percent of subjects improved/worsened} = \frac{(\text{number of subjects improved/worsened from baseline})}{\text{total number of subjects}} \times 100$$

Comparison between the study treatments will be made in terms of changes from baseline. The null hypothesis, that the mean change from baseline is equal between the 2 study treatments at post-baseline time point, will be tested using methods described in the Statistical Analysis Plan table.

Statistical Analysis Plan

Evaluation	Change from Baseline	Comparisons between study treatments	Notes/Interpretation
Ultrasound measurement ○ Aggregate size	Paired t-test; If normality fails, a Wilcoxon signed-rank test will be used.	Wilcoxon rank-sum test or sample t-test	N/A

Protocol Version 2:

This document contains confidential, proprietary information.

Volume change by 3D imaging analysis	Paired t-test; If normality fails, a Wilcoxon signed-rank test will be used.	Wilcoxon rank-sum test or sample t-test	A higher value reflects an improvement in skin volume.
--------------------------------------	------------------------------------------------------------------------------	-----------------------------------------	--------------------------------------------------------

Questionnaires will be tabulated, and the percentage of all response options will be reported for each question.

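### The between-product tests treat the two cheeks of one subject as independent groups, although the split-face design makes the data paired

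*Combined protocol and SAP*

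**What the plan says.** The Synopsis describes a "Randomized, split-face, subject-blinded, comparative study". Section 8.1.1, step 8, has site staff "assign the appropriate test treatment to each side of the face based on the predetermined computer-generated randomization". Sections 9.2 and 9.3 measure 3D volume and ultrasound on the left and right cheek of each subject. Section 7.5 requires the same type of injection tool on both sides: "Switching device within the subject will not be allowed in order to avoid any inconsistent comparison".

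Section 10 states the between-product hypothesis as "The null hypothesis, that the mean change from baseline is equal between the 2 study treatments at post-baseline time point". In the Statistical Analysis Plan table, the column for comparisons between treatments reads "Wilcoxon rank-sum test or sample t-test" for both aggregate size and 3D volume change. The neighbouring column, for change from baseline within a product, reads "Paired t-test; If normality fails, a Wilcoxon signed-rank test will be used". The analysis uses completers only, and Section 6.1 plans for 15 of them. Questionnaire answers are tabulated without a test.

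**The concern.** Each completing subject contributes one change score per product, and the two scores come from the same face. They form a pair, and the protocol treats them as one when it holds the injection tool constant within the subject. The rank-sum test ignores that link, as does a t-test if it is the two-sample version.

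Section 5.1 makes comparison of the two fillers the study objective, and these two cells hold the only between-product tests. If a subject's two cheeks respond alike, an unpaired test is too conservative: a real product difference can be missed, and a finding of no difference is hard to interpret. If the two cheeks vary in opposite directions, false positives exceed the nominal level. The cell also gives no rule for choosing between its two tests, so the choice could be made after the data are seen.

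**Working it through.** The plan gives no alpha, power, effect size, SD or sample-size calculation, so it has no figure of its own to reproduce. The check compares unpaired with paired tests on the planned number of pairs.

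**Inputs from the documents.** 15 completers (Section 6.1), completers-only analysis (Section 10) and one product per cheek (Section 8.1.1). This gives n = 15 pairs.

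**Assumptions, not in the documents.** Two-sided alpha 0.05; bivariate normal change scores with equal SDs; true difference d of 0, 0.5, 0.75 or 1.0 SD of change; rho from -0.3 to 0.7.

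**Step 1: standard errors.** In SD units, the difference in means has true variance 2(1 - rho)/15. The two-sample formula uses 2/15 whatever rho is. The two agree only at rho = 0. The ratio of unpaired to paired 95% CI width is approximately

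t(0.975, 28) / [t(0.975, 14) × √(1 - rho)] = (2.048 / 2.145) / √(1 - rho) = 0.955 / √(1 - rho).

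This is 1.14 at rho 0.3, 1.35 at rho 0.5 and 1.74 at rho 0.7.

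**Step 2: paired t power at 0.75 SD.** Noncentral t with 14 df and ncp = 0.75 × √15 / √(2(1 - rho)) = 2.905 / √(2(1 - rho)):

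- rho 0: 2.905 / 1.414 = 2.054, power 48.1%
- rho 0.3: 2.905 / 1.183 = 2.455, power 62.7%
- rho 0.5: 2.905 / 1.000 = 2.905, power 77.1%
- rho 0.7: 2.905 / 0.775 = 3.750, power 93.6%

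**Step 3: all four tests at 0.75 SD.** Simulation with at least 100,000 runs per setting:

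| rho | two-sample t | rank-sum | paired t | signed-rank |
|---|---|---|---|---|
| 0.3 | 51% | 47% | 63% | 60% |
| 0.5 | 51% | 47% | 77% | 75% |
| 0.7 | 52% | 47% | 94% | 92% |

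**Step 4: other effect sizes, rho 0.3 / 0.5 / 0.7.**

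- d = 0.5 SD: two-sample t 23 / 20 / 15%; paired t 33 / 44 / 64%.
- d = 1.0 SD: two-sample t 79 / 82 / 87%; paired t 86 / 95 / over 99%.

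**Step 5: type I error (d = 0).**

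| rho | two-sample t | rank-sum | paired t |
|---|---|---|---|
| -0.3 | 8.4% | 7.7% | 5.0% |
| 0.3 | 2.1% | 2.0% | 5.0% |
| 0.5 | 0.8% | 0.8% | 5.0% |
| 0.7 | 0.1% | 0.2% | 5.0% |

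**Step 6: where pairing does not add power.** At 0.75 SD and rho 0, the two-sample t-test has 50.9% power against 48.1% for the paired t-test. The two are level, at 51.0%, near rho 0.07. At rho -0.3 the two-sample t-test shows about 51% against 39%, but part of that lead comes from its inflated type I error.

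**The case against.** The strongest reply is that only half of the cell is definitely wrong. The t-test could mean a one-sample test on within-subject differences, or a paired test with a word missing, and either would be valid. If that is what would be used, the two-sample figures above do not apply. This stands as a point about the t-test. It does not rescue the cell, which would then offer one valid and one invalid test with no rule for choosing. The rank-sum entry is explicit in both rows, and the neighbouring column shows that the authors distinguish it from signed-rank.

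Second, every magnitude rests on an assumed rho and alpha. This is true. Section 7.5 says that the amount of product needed "varies between subjects and within subjects bilaterally, given the natural asymmetry of the face". Variation between subjects would tend to raise rho and left-right asymmetry to lower it. The sentence concerns the amount injected, not change scores, so it settles nothing. Pairing therefore cannot be promised to raise power at every rho. The firmer argument is validity: under the stated model the paired t-test holds its level whatever rho is.

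Third, the study has 15 subjects, no designated primary endpoint and no power target, and the per-cheek data would allow a paired re-analysis later. That limits the damage. But the plan states formal null hypotheses, so the test it names should be valid for the design, and a corrected test chosen after the data are seen carries less weight.

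**Conclusion.** The concern holds. As written, the plan allows an independent-groups test for the study's central comparison, on data that are paired by design, and no other section supplies a paired method for comparing the products. The size of the error depends on rho. For rho of 0.3 to 0.7 and a 0.75 SD difference, the loss is about 12 to 42 percentage points of power for two-sample against paired t (63 - 51 = 12; 94 - 52 = 42). At rho of -0.3, type I error is about 8.4% (two-sample t) or 7.7% (rank-sum) instead of 5%. Near rho of zero little changes. These figures assume two-sided alpha 0.05, normal change scores, equal SDs and 15 pairs. The finding that the rank-sum test does not fit the design needs none of those assumptions. This should be corrected before analysis.

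**What to change.** In both rows of the Section 10 table, replace the entry for comparisons between treatments with the following: for each subject, take the change from baseline on the Restylane Contour side minus that on the Juvéderm Voluma side; test the mean of these differences by paired t-test, or by Wilcoxon signed-rank test if normality of the differences fails. Report the mean paired difference, ideally with its 95% CI. State the alpha and sidedness in the same edit, since the plan gives neither.

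The cost is two table cells and a sentence of SAP wording. No extra subjects, measurements or procedures are needed, because both outcomes are already recorded per cheek.

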11. ADVERSE EVENTS

Throughout the course of the study, all adverse events will be monitored and reported on an adverse event CRF/eCRF without omitting any requested and known information. When AEs occur, the main concern is the safety of the study subjects. At time of the informed consent signature, each subject must be given the name and phone number of investigational site personnel for reporting AEs and medical emergencies.

At each visit, after the subject has had the opportunity to spontaneously mention any problems, the investigator should inquire about AEs by asking the standard questions:

- “Have you had any health problems since your last study visit?”
- “Have there been any changes in the medicines you take since your last study visit?”

AEs should be reported for any clinically relevant change, as determined by the Investigator, in concomitant medication(s) that is the result of an untoward (unfavorable and unintended) change from baseline in a subject’s medical health following exposure to the study treatment.

Changes from baseline in any protocol-specific parameter evaluated during the study are to be reviewed by the Investigator. In addition, the subject’s responses to any questionnaire utilized during the study are to be reviewed by the investigator. Any untoward (unfavorable and unintended) change from baseline in a protocol-specific parameter or question response that is clinically relevant, in the opinion of the investigator, is to be reported as an AE. These clinically relevant changes will be reported regardless of causality.

11.1 Definitions

11.1.1. Adverse Events (AE)

An adverse event (AE) is defined as any untoward medical occurrence in a subject taking part in the clinical study, and which does not necessarily require a causal relationship with the investigational product and/or a clinical trial procedure.

An AE can be any unfavourable and unintended sign (including an abnormal laboratory value), symptom, or disease temporally associated with the use of the investigational product, whether or not related to this product.

When an AE has a likely or very likely causal relationship with the investigational product and/or a clinical trial procedure, it is named undesirable effect or related AE (see Section 3).

11.1.2. Local tolerability signs and symptoms (only applicable for cosmetic safety studies)

In cosmetic studies, local skin tolerability includes some expected functional and/or physical signs on the application area, observed by the Investigator or reported by the subjects (see Appendix). Those signs are collected in the final report based on scales or a diary. If the severity of a local skin tolerability sign or symptom, is such that the product application is

Protocol Version 2:

This document contains confidential, proprietary information.

Protocol GLI.04.US.SL.015

CONFIDENTIAL

permanently discontinued and/or a corrective concomitant treatment (except moisturizer or emollient) is prescribed, it is recorded as an undesirable effect (related AE).

11.1.3. Serious Adverse Events (SAE) and serious undesirable effect/related SAE

A Serious Adverse Event (SAE) is any adverse event which results in death, is life-threatening, requires inpatient hospitalization or prolongation of existing hospitalization, results in persistent or significant disability/incapacity, or is a congenital anomaly/birth defect.

Notes:

The term “immediate vital risk” refers to an event in which the subject was at risk of death at the time of the event; it does not refer to an event that hypothetically might have caused death if it was more severe.

Inpatient hospitalization is considered to have occurred if the subject has had to stay for a night at the hospital. Hospitalization solely for the purpose of a diagnostic test (even if related to an AE), elective hospitalization for an intervention that was already planned before subject enrolment in the clinical trial, admission to a day-care facility, social admission (e.g., if the subject has no place to sleep), or administrative admission (e.g., for a yearly examination) should not be considered as a SAE.

A serious undesirable effect/related SAE is defined as any SAE which the Investigator classifies as having a reasonable possibility for a causal relationship with the investigational product and/or the clinical trial procedure.

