11.4.1. Management and reporting procedures for undesirable effects (i.e. related adverse events)

Undesirable effects should be recorded in the CRF and summarized in the report in a summary table with at minimum the subject number, AE number, AE diagnosis or signs and symptoms, location, date of onset, seriousness, severity, action taken, relationship, date of resolution and concomitant treatment associated as well as a detailed narrative of the event.

In addition, based on his/her medical judgment, the Investigator will assess whether an undesirable effect requires immediate (i.e. within 24 hours) reporting to the Sponsor. In such cases, the summary table will be sent to the Sponsor, along with the AE narrative and any other relevant information (concomitant treatments, product weighing, ...).

All undesirable effects should be appropriately documented, i.e. any relevant information such as demographics, medical history and concomitant therapies should be recorded in the CRF.

The Investigator is to monitor and record the progress of the adverse effect until the last subject's study visit.

The Investigator is to update the AE narrative as appropriate, each time follow-up information is collected and when the final outcome of the adverse effect is known.

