11.4.2. Management and reporting procedures for Serious Adverse Events

The Investigator is to take the following steps:

Protocol Version 2:

This document contains confidential, proprietary information.

Protocol GLI.04.US.SL.015

CONFIDENTIAL

1. Take prompt and appropriate medical action, if necessary. The safety of clinical trial subjects is the first priority
2. Ensure the AE is classified as an SAE. Immediately inform the Sponsor's representative of the event by email or fax (see contact details below) and discuss further actions to be taken:

e-mail: [contact]

3. Complete the Serious Adverse Event (SAE) form provided by the Sponsor's representative **Within 24 hours**, fax or send by e-mail **to the Sponsor's representative** the completed SAE form, accompanied any other relevant information (e.g. test results or medical records).
4. Monitor, record and send to Sponsor's representative the progress of the event until it resolves or reaches a stable outcome, with or without sequelae (send the updated SAE form with follow-up information and any other relevant information to Sponsor's representative).
5. Obtain and maintain in the subject's file all pertinent medical records, information, and medical judgments from colleagues who assisted in the treatment and follow-up of the subject. If necessary, contact the subject's personal physician or hospital staff to obtain further details.
6. If applicable, comply with the regulatory requirement(s) related to the reporting of SAEs to the Institutional Review Board (IRB) / Independent Ethics Committee (IEC).

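### The SAE definition omits events where intervention averted serious harm and excludes solely diagnostic admissions prompted by an AE, so neither triggers the mandatory 24-hour report

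*Combined protocol and SAP*

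**What the plan says.** Section 11.1.3 defines an SAE as an AE that "results in death, is life-threatening, requires inpatient hospitalization or prolongation of existing hospitalization, results in persistent or significant disability/incapacity", "or is a congenital anomaly/birth defect". The list ends there.

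The notes below it set the threshold for admission: "Inpatient hospitalization is considered to have occurred if the subject has had to stay for a night at the hospital". They then list admissions that do not count. The first is "Hospitalization solely for the purpose of a diagnostic test (even if related to an AE", and the sentence closes with "should not be considered as a SAE".

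Two routes lead to a 24-hour notice of an AE:

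- **Section 11.4.2 (mandatory).** The investigator is to "Ensure the AE is classified as an SAE", inform the sponsor's representative immediately, and send the completed SAE form "Within 24 hours".
- **Section 11.4.1 (discretionary).** For undesirable effects, "the Investigator will assess whether an undesirable effect requires immediate (i.e. within 24 hours) reporting to the Sponsor". The basis is medical judgment, and no trigger is listed.

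Section 11.1.1 reserves the term undesirable effect for AEs with a likely or very likely causal relationship to the product or a trial procedure. Section 11.3 has five causality grades; *not clearly attributable* is the next one down.

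**The concern.** The definition looks at outcome only. If an event is dangerous but is treated in time, the outcome that would have made it serious does not occur, and no criterion asks what the intervention was for. The more successful the treatment, the less likely the event is to be classed as serious.

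The diagnostic exclusion adds to this. The other exclusions in the same sentence (pre-planned, day-care, social and administrative admissions) are not defined by a new AE. The diagnostic one reaches admissions that an AE did prompt, because the parenthesis says so.

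At stake are the speed at which the sponsor hears of such an event, how long it is followed, and whether it appears as serious in the report. The trial compares two fillers within each subject and enrols a minimum of 15. At that size one event more or less in the SAE count is 1/15 = 6.7% of subjects, so classification matters to the safety description of either product.

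**Working it through.** No formula applies; the check is to follow cases through the text. I also read the rest of Section 11, including local tolerability (11.1.2), severity (11.2) and pregnancy (11.5), for another seriousness criterion or another mandatory expedited route for AEs, and found none. Section 11.1.2, headed as applying to cosmetic safety studies only, would record a local sign needing corrective treatment as a related AE, not as an SAE.

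| Case | Meets 11.1.3? | 24-hour notice | Follow-up |
|---|---|---|---|
| A. Treated as an outpatient before any significant incapacity, life threat or admission; rated likely or very likely related | No | Investigator's discretion (11.4.1) | To the last study visit (11.4.1) |
| B. As A, but rated not clearly attributable | No | None | None specified |
| C. Overnight stay solely for tests prompted by an AE, no other criterion met | No, by the exclusion | As A or B, by causality grade | As A or B |
| D. Overnight stay that includes treatment | Yes | Mandatory (11.4.2) | Until resolved or stable (11.4, 11.4.2) |
| E. Significant incapacity that is later reversed | Can qualify, since the criterion is persistent *or* significant | Mandatory if so classed | As D |

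Three things follow.

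1. **The gap is cases A to C.** Cases D and E are covered by the present text.
2. **Causality grading decides whether even the discretionary route exists.** In case C the cause may still be under investigation when the event is graded, so a grade below likely is plausible at that point.
3. **More than the 24-hour clock is tied to the SAE label.** Follow-up until resolved or stable (11.4 and 11.4.2 step 4), notice to the sponsor after the subject has completed (11.4), and the IRB/IEC reporting step (11.4.2 step 6) are all written for SAEs only.

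**The case against.** The strongest reply is that such events would not disappear. Section 11 requires all AEs to be recorded. Section 11.4.1 asks, for related events, for a table with seriousness, severity and action taken, plus a detailed narrative. Section 13.1 provides for close monitoring. A careful investigator can report within 24 hours without being obliged to. All of this stands, and it limits the point: a related event would be visible in the report, and what is lost is the obligation to report early and the SAE-level follow-up. It helps less in case B, because the discretionary route and the narrative are written for related events.

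A second reply is that the sponsor's SAE form, or the GCP and ICH guidelines under which Sections 12.1 and 13.1 place the study, may supply the missing criterion. The form is not in the documents and no outside definition is reproduced, so this cannot be checked. An investigator working from the protocol would apply Section 11.1.3 as it stands.

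Three stronger readings are tempting but are not supported:

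- *Any averted or reversed complication escapes the definition.* It does not. The criterion includes significant as well as persistent disability, so a transient but significant loss of function can qualify.
- *Any overnight stay for investigation is excluded.* The exclusion says solely. A stay that includes treatment counts, as does an event that meets another criterion.
- *The sponsor would hear only at the next visit, Day 28 or Day 168.* Those are intervals between subject visits, not delays in notice to the sponsor. Subjects are told at Day 0 when to contact the investigator (8.1.1, item 12) and are given a telephone number for reporting (Section 11). The definition of an SAE does not alter those intervals.

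**Conclusion.** The point holds in a limited form. The SAE list is closed and has no criterion for intervention that prevented a serious outcome. It also excludes a purely diagnostic admission prompted by an AE. Events in either group have no mandatory 24-hour report. Those rated likely or very likely related have a discretionary one; those rated lower have none.

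The size cannot be expressed as a rate. The documents give no frequency for such complications and do not describe which ones might occur, so I assume only that one is possible. Section 4 notes that these fillers can be reversed with hyaluronidase, which makes treatment before lasting harm foreseeable, but no more than that. The conclusion rests on the internal text of Sections 11.1.1, 11.1.3, 11.4, 11.4.1 and 11.4.2, not on any outside definition of an SAE. The correction is worth making because it is short and bears on safety reporting.

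**What to change.** Amend Section 11.1.3 in two places.

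1. Add to the definition: *or requires medical or surgical intervention to prevent death, a life-threatening condition, or persistent or significant disability/incapacity*. Do not extend this to preventing hospitalization, or ordinary outpatient care given to avoid an admission could become an SAE.
2. Reword the first exclusion to: *Hospitalization solely for a diagnostic test not prompted by an adverse event*. Deleting the parenthesis alone would change nothing, because every solely diagnostic admission would still be excluded.

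While the section is open, reconcile it with Sections 11.1.1, 11.4.1 and 11.4.2. Also remove or connect the note on *immediate vital risk*, a term that the definition does not use. The existing procedure in Section 11.4.2 then applies to the added events without further change.

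The cost is one clause and one reworded phrase in an amendment, with IRB approval under Section 13.4. There may be a few more expedited reports; the number cannot be derived from the documents. The change affects classification and reporting only, not treatment.
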